7.7.4.1.3. CSF Iduronidase Assay

A portion of the CSF (~2-4 cc) will be frozen and, if applicable, shipped on dry ice to the Harbor-UCLA laboratory for subsequent assay of iduronidase activity by fluorometric assay. 25 μ l CSF will be incubated at 37° C for 1 h with 25 μ l of 6mM 4-methylumbelliferyl α -L iduronide substrate. The reaction will be stopped with 1 ml glycine carbonate buffer (400 mM, pH 10). Samples will be read by spectrofluorometer, wavelength 365 excitation/440 emission. Iduronidase activity is expressed in nmol of converted substrate per hour per ml CSF.

7.7.4.1.4. CSF ELISA for α -L-iduronidase specific antibodies

A portion of the CSF (~ 2-4 cc) collected will be frozen and shipped on dry ice to a specialty laboratory for subsequent anti-iduronidase antibody analysis. Antibodies specific for iduronidase are detected by standard ELISA protocol using anti-human IgG labeled with alkaline phosphatase as the secondary antibody.

7.7.4.1.5. Additional CSF

The remainder of the CSF collected (~ 2-6 cc) may be frozen and stored at the LAB-HUCLA for future studies.

7.7.4.2. Serum analyses

7.7.4.2.1. Serum ELISA for α -L-iduronidase specific antibodies

Blood samples are collected from each subject in a serum separator tube at baseline and at three month intervals. Approximately 2.5-5 cc of blood will be collected. These samples spun down and the serum quick frozen, then shipped on dry ice to Harbor-UCLA Medical Center (Torrance, CA) for subsequent anti-iduronidase antibody analysis. Antibodies specific for iduronidase are detected by standard ELISA protocol using anti-human IgG labeled with alkaline phosphatase as the secondary antibody.

7.7.4.2.2. Complete blood count (CBC) and serum chemistries

Standard blood specimens for CBC and comprehensive metabolic panel chemistries will be collected in the institution-specific tube and analyzed by the local laboratory. The serum chemistries will evaluate electrolytes (sodium, potassium, chloride, calcium), bicarbonate, glucose, BUN, creatinine, magnesium, phosphate, hepatic enzymes (AST and ALT), total protein, albumin, bilirubin, and alkaline phosphatase. Other chemistries may be obtained if clinically indicated in the opinion of the investigator.

7.7.4.2.3. Coagulation studies

Standard blood specimens for prothrombin time (PT), partial thromboplastin time (PTT), and international normalized ratio (INR) will be collected in the institution-specific tube and analyzed by the local laboratory.

7.7.5. Neurophysiologic evaluation

7.7.5.1. CSF flow study

At baseline screening, the subject will undergo a CSF flow study. This study is performed by injecting radionuclide (e.g. 99m Technetium-DTPA) into the lumbar cistern. Access to the lumbar cistern may require fluoroscopic-guided assistance due to body habitus or disease-related changes to the lumbar bony and ligamentous structures. Images will be obtained using a scintillation camera as the radionuclide flows caudally. Time to appearance of the radionuclide to specific CSF compartments will be compared to established norms (Chamberlain 1998). This study will guide our decision as to whether a lumbar approach for the intrathecal injection can be performed.

7.7.6. Investigator global assessment

At each study assessment, the Principal Investigator will use data from the clinical assessments, laboratory studies, neurophysiologic assessments, and imaging studies to assign a global assessment score to each subject. Each score will be assessed in comparison to the subject's baseline. Scoring will be done as follows:

- +3 – Marked improvement
- +2 – Moderate improvement
- +1 – Mild improvement
- 0 – No change
- 1 – Mild decline
- 2 – Moderate decline
- 3 – Marked decline

The Principal Investigator will be asked to justify the decision in a comment section on the CRF.

7.8. Safety and Outcome Endpoints

Safety will be monitored continuously throughout the subject's study participation through recording all adverse events (AEs) and periodically performing clinical and laboratory evaluations. Also refer to Section 11.6 for a description of a Data

and Safety Monitoring Board for additional evaluation of the endpoints described below.

7.8.1. Safety Endpoints

7.8.1.1. History and Physical Examination

A detailed and thorough medical history will be obtained at screening as described in the methods. Data will be qualitative.

A detailed and thorough physical examination will be performed at each visit as described in the methods. Data will be qualitative.

If clinically significant worsening from the baseline medical status or vital signs status is noted, the change will be documented as an AE on the appropriate data collection sheet and will be followed as an adverse event consistent with the procedure outlined in Section 11.3. Clinically significant worsening is defined as variation decline in physical findings that has medical relevance and results in an alteration in medical care.

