We propose an extension of our study to examine the long-term effects of intrathecal enzyme replacement on cognition. In order to document improvement with intrathecal ERT, neuropsychological testing, clinical testing, and imaging modalities will be employed. Multiple cognitive domains will be tested with an established battery of neuropsychological tests that have documented validity in patients with storage diseases (Shapiro et al., 2006). Magnetic resonance imaging of the brain will be used to document abnormalities and changes in volume and morphology. In addition, brain diffusion tensor imaging (DTI) will be employed to characterize diffusion abnormalities and perform fiber tracking. DTI and fiber tracking register diffusion patterns of water to follow axonal transport in the brain. Preliminary results in attenuated MPS I patients show DTI and fiber tracking to be abnormal in some patients (Fig. 3, Shapiro et al., 2012). DTI has been used to quantify improvement following hematopoietic stem cell transplantation in the lysosomal storage disorder, Krabbe disease (Provenzale et al., 2005).

Fig. 3: FA maps for MPS IH and MPS IA participants matched for age and gender. The figures below show the assigned colors for FA in the white matter tracts for the following directions: red = medio-lateral (left–right), green = anterior–posterior (front–back) and blue = superior–inferior (up–down). Data below the figure are from these two participants. (Shapiro et al., Mol Genet Metab 2012)

To summarize, many people with mild and moderate forms of MPS I suffer from cognitive decline, poor performance in school, and behavior difficulties. There is essentially no treatment for these problems. These patients are not candidates for hematopoietic stem cell transplantation, and intravenous enzyme replacement therapy does not treat these central nervous system symptoms. Data from the canine model of MPS I show that intrathecal rhIDU can penetrate the brain, spinal cord, and meninges, reducing GAG storage to normal levels. Data from human subjects have shown that intrathecal therapy is safe, and that it leads to clinical improvement in spinal cord compression symptoms and signs on neurologic examination. In this study, we plan to extend the evaluation of IT rhIDU to the stabilization or reversal of cognitive decline in MPS I patients.

3. Setting of the Human Research

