7.8.1.2.2. Complete blood count and chemistries

Blood for a complete blood count and serum chemistries (including basic chemistries, liver function tests, renal function tests) will be performed according to the schedule above. Analyses will be performed at a local clinical laboratory. Age-appropriate normal values for the laboratory will be used for comparison.

The investigator must score all abnormal laboratory values as either clinically significant (CS) or not clinically significant (NCS). Some laboratory values may be outside of the normal value range because of the underlying disease. As in routine practice the investigator should use clinical judgment when considering clinical significance. Clinical significant worsening is defined as any variation in laboratory parameters that has medical relevance and results in an alteration in medical care.

If clinically significant laboratory worsening from baseline is noted, the changes will be documented on the appropriate adverse event form and will be followed as an adverse event consistent with the procedure outlined in Sections 11.1,

11.2, and 11.3. The investigator will also assess the relationship of all clinically significant abnormal values to program drug as being none, remote, possible, probable, or definite.

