7.8.2.3.2. Neurologic examinations

A full neurologic examination including mental status, cranial nerves, motor, sensory, associated motor, and reflexes will be conducted at each visit throughout the study period (refer to Section 7.7.3.2 for further information). Data will be qualitative.

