9.3.3.2. History and physical examination

At each visit, each subject will be classified as experiencing an adverse event if clinically significant worsening from baseline medical status, as described in Section 7.8.1.1, has occurred. The frequency and percent of subjects experiencing such an event will be tabulated for each visit.

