12.1. Adverse Events

Subjects in this study will be closely monitored during the enzyme administration and for one hour afterward with frequent (every 15 minutes) vital signs and continuous pulse oximetry. The subject will be able to contact the investigator or other appropriate personnel to report adverse events occurring later. These will be treated with appropriate medical care where applicable. Adverse events that are unanticipated will be reported within 10 working days to the institutional review board.

An adverse event (AE) is any undesirable physical, psychological or behavioral effect (an unfavorable and unintended sign, symptom or disease) experienced by a subject during their participation in an investigational study whether or not product-related. This includes any untoward signs or symptoms experienced by the subject from the time of signing of the informed consent until completion of the study. Adverse events may include, but are not limited to:

- Subjective or objective symptoms spontaneously offered by the patient or subject and/or observed by the investigator or medical staff.
- Laboratory abnormalities of clinical significance.
- Disease signs, symptoms and/or laboratory abnormalities already existing prior to the use of the study medication are not considered adverse events after treatment unless they reoccur after the subject has recovered from the pre-existing condition or they represent an exacerbation in intensity or frequency.

All reportable AEs will be assigned a relationship to the study drug by the principal investigator. A drug-related AE is an event with a plausible time relationship to drug intake that cannot be explained by the disease or other drugs.

Any AEs experienced by the subject, from the time of signing the Informed Consent Form through the completion of study participation, will be reported as described (see Section 11.3) and recorded on the CRF. If AEs are present when the patient completes study participation, the subject will be re-evaluated within two weeks of completion and the results of this re-evaluation will be recorded on the CRF. If AEs are not resolved, additional follow-up will be performed as appropriate. All reportable AEs must be reported to the RDCRN within **20 working days** of the notification of the event or of the site becoming aware of the event.

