12.2. Serious Adverse Events

A serious adverse event (SAE) is defined as any adverse event that results in any of the following outcomes:

- Death
- Life-threatening experience
- Required or prolonged inpatient hospitalization
- Persistent or significant disability/incapacity
- Congenital anomaly/birth defects

Life-threatening experience: Any adverse event that places the patient, in the view of the reporter, at immediate risk of death from the adverse event as it occurred, i.e., does not include an adverse event that had it occurred in a more severe form, might have caused death.

Persistent or significant disability/incapacity: The adverse event that resulted in a substantial disruption of a person's ability to conduct normal life functions.

Important medical events based upon appropriate medical judgment, that may jeopardize the patient or subject and may require medical or surgical intervention to prevent one of the outcomes listed above: Adverse events that may not result in death, be life-threatening, or require hospitalization may be considered a serious adverse event when, based upon appropriate medical judgment, they

may jeopardize the patient or subject and may require medical or surgical intervention to prevent one of the outcomes listed above.

The investigator will be asked to assess the severity of the adverse drug/biologic experience using the following categories: mild, moderate and severe. This assessment is subjective and the investigator should use medical judgment to compare the reported adverse event to similar type events observed in clinical practice. Below are listed guidelines for severity assessment:

- **Mild:** Symptom(s) barely noticeable to the subject/patient or does not make the subject/patient uncomfortable. The adverse event does not influence performance or functioning. Prescription drugs are not ordinarily needed for relief of symptom(s).
- **Moderate:** Symptom(s) of a sufficient severity to make the subject/patient uncomfortable. Performance of daily activities is influenced. Treatment of symptom(s) may be needed.
- **Severe:** Symptom(s) of a sufficient severity to cause the subject/patient severe discomfort. Severity may cause cessation of treatment with the study drug. Treatment for symptom(s) may be given.

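### The per-visit examination AE table counts worsening only if it changed medical care, which conflicts with the protocol's own AE definition, and the neurologic examination has no named place in the safety analysis

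*Combined protocol and SAP*

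**What the plan says.** Section 7.8.1.1, under Safety Endpoints, defines the threshold: "Clinically significant worsening is defined as variation decline in physical findings that has medical relevance and results in an alteration in medical care". Sections 7.7.3.1 and 7.8.2.3.1 carry the same two-part test, medical relevance plus a change in care. The analysis plan takes it up in 9.3.3.2: at each visit "each subject will be classified as experiencing an adverse event if clinically significant worsening from baseline medical status", as described in 7.8.1.1, has occurred, and the number and percentage of such subjects are tabulated by visit.

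The blood count and chemistry endpoint (7.8.1.2.2) uses a parallel test: "Clinical significant worsening is defined as any variation in laboratory parameters that has medical relevance and results in an alteration in medical care". Section 9.3.3.3 tabulates on it.

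The general definition in 12.1 is wider: "An adverse event (AE) is any undesirable physical, psychological or behavioral effect (an unfavorable and unintended sign, symptom or disease". It makes no reference to care. It also counts a pre-existing sign that becomes more intense or more frequent. For laboratory findings, however, it lists only abnormalities of clinical significance. Section 12.2 has a Mild grade for events that do not affect functioning and ordinarily need no prescription drug.

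The neurologic examination is done at every visit (Table 1; 7.7.3.2). It is listed under outcome endpoints in 7.8.2.3.2, with the note "Data will be qualitative".

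**The concern.** Long-term safety of intrathecal dosing is the first objective, and 9.1 names calculation of AE rates as a statistical goal. A table meant to show what happened to subjects should not depend on what the clinician then did. Under 9.3.3.2 two subjects with the same new sign at the same visit can be classified differently because one had a change in management and the other was observed.

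Relative to 12.1, the extra condition can only remove subjects from the examination table, so any error runs toward apparent safety. Two definitions of the same term also invite sites to record differently. An investigator who reads 7.8.1.1 may decide that an observed-only sign is not clinically significant and not enter it at all.

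The neurologic gap is a separate matter. The examination closest to the dosed compartment is the one for which the safety section sets no worsening rule and names no table.

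**Working it through.** The plan gives no AE rate or other figure on this point, so there is nothing to reproduce. The check is a comparison of the texts, followed by a short calculation of how sensitive the tables are.

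**1. Same finding, two definitions.** Take a new sign on physical examination that is medically relevant and is watched without any change in care.
- 12.1: unwanted sign, no care condition. It is an AE.
- 12.2: it can be graded Mild.
- 7.7.3.1, 7.8.1.1, 7.8.2.3.1: no change in care, so not clinically significant.
- 9.3.3.2: the subject is not classified as having an AE at that visit.
- 9.3.3.4 (Other Adverse Events): no care condition, so the event could be counted here. The text does not say that findings failing the 7.8.1.1 test belong here.

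**2. Laboratory findings.** 7.8.1.2.2 and 9.3.3.3 apply the care-dependent test to blood count and chemistry. But 12.1 also restricts laboratory AEs to clinically significant ones, so the conflict is weak. CSF glucose, protein and cell counts are analysed in 9.3.3.1 as change and out-of-range frequency, with no filter.

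**3. Neurologic examination.** The physical-examination components in 7.7.3.1 run from general appearance to extremities and joints, with no neurologic item. Section 7.8.1 lists history and physical examination, CSF, and blood tests. The four categories in 9.3.3 are CSF and antibody, history and physical examination, blood tests, and other AEs. On the outcome side, 9.3.4.2.3 takes only the MMSE from the neurologic examination. Cranial-nerve, motor, sensory and reflex findings therefore have no named table in either analysis.

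**4. Sensitivity of a visit table.** Section 9.2 gives at most 6 subjects. Section 4 expects 67% to enrol: 0.67 × 6 = 4.02, about 4.
- Weight of one subject: 100/6 = 16.7 percentage points, or 100/4 = 25.
- Upper two-sided 95% exact limit when none is classified: 1 − 0.025^(1/n) = 45.9% for n = 6 and 60.2% for n = 4.

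**5. Illustration on assumed inputs.** Let p be the share of subjects with true worsening at a visit and c the share of those whose care changes. Neither is in the documents. The chance that the table shows at least one subject is 1 − (1 − pc)^n. For n = 6 and p = 0.33:
- c = 1 (no filter): 0.91
- c = 0.5: 0.66
- c = 0.25: 0.40

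Over p = 0.17 to 0.50 the chance is 0.67 to 0.98 at c = 1 and 0.23 to 0.55 at c = 0.25. The proportion lost from this table is simply 1 − c, so it cannot be estimated from the documents.

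**The case against.** The strongest reply is that nothing need be lost. Section 7.8.1.1 says that qualifying worsening is documented as an AE; it does not say that other worsening is not one. Section 7.8 opens by requiring all AEs to be recorded, 12.1 and 12.3 require them on the CRF, 12.7 sends all AEs with severity and attribution into the periodic report, and 9.3.3.4 tabulates other AEs with no care condition. This largely stands. A reader might infer that observed-only worsening disappears from the safety endpoint, and the documents do not support that. What they show is omission from the 9.3.3.2 table, with an unstated destination.

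A reader might likewise infer that neurologic worsening has no route into AE reporting. That is also too strong. A new neurologic sign meets 12.1 and can be tabulated under 9.3.3.4, and new neurologic symptoms or signs at the post-discharge visit lead to re-hospitalization (7.6), which is itself a change in care. The interim history also touches neurologic status. What remains is that the examination has no named safety endpoint or table.

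The Background's remark that "There is essentially no treatment for these problems" might suggest that untreatable worsening can never pass the filter. It refers to cognitive decline, school performance and behavior, not to neurologic signs in general. Cognition is also measured without any care filter through the Hopkins test and the MMSE. Finally, a mild event that needs no prescription drug may still involve some change in care, a term the protocol leaves undefined, so the Mild grade is supporting evidence rather than proof.

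**Conclusion.** The point holds as a conflict between stated rules. The examination threshold in 7.7.3.1, 7.8.1.1 and 7.8.2.3.1, carried into 9.3.3.2, is narrower than the AE definition in 12.1. It makes the per-visit examination table depend on the clinician's response. The possible bias is downward. Its size is unknown, and the figures in step 5 of the working are illustrations, not estimates. With four to six subjects, a single omission is large on the scale of one table.

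The same test governs the blood count and chemistry table, but the conflict there is weak. The absence of the neurologic examination from 7.8.1 and 9.3.3 is a separate gap and follows directly from the text. The conclusion assumes that 9.3.3.4 is not already understood to absorb findings that fail the 7.8.1.1 test; if it is, the remaining defect is one of presentation and consistency between sites. This should be corrected, but it does not show that safety events go unreported.

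**What to change.** - Reconcile the passages by using the 12.1 AE definition for examination worsening in 7.7.3.1, 7.8.1.1, 7.8.2.3.1 and 9.3.3.2.
- Record change in care as a separate CRF attribute of each event, not as a condition for counting it. Section 12.3 already asks for corrective treatment, so this is a small addition.
- Add worsening from baseline on the neurologic examination to 7.8.1 and to the 9.3.3.2 table.
- State that 9.3.3.4 covers all AEs not counted in the preceding safety tables.
- For blood count and chemistry, say whether clinical significance in 12.1 is meant to include a change in care.
- Correct the cross-references at the same time: 9.3.3.3 cites 7.8.1.2.4, but the definition is in 7.8.1.2.2; the AE procedures cited as 11.1 to 11.3 are in 12.1 to 12.3.

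The cost is protocol wording and one CRF field. The examinations are already done at every visit, and no clinical management rule changes. The downside is that more mild AEs will be listed.

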7.8.1.2. Laboratory Evaluations

7.8.1.2.1. CSF chemistry and cell counts

Glucose, protein, and cell counts will be recorded in their standard units. The subject's levels will be compared to age-matched normative controls from that laboratory. Data will be kept as quantitative, continuous variables, and each subject assessed for change over the study period.

7.8.1.2.2. Complete blood count and chemistries

Blood for a complete blood count and serum chemistries (including basic chemistries, liver function tests, renal function tests) will be performed according to the schedule above. Analyses will be performed at a local clinical laboratory. Age-appropriate normal values for the laboratory will be used for comparison.

The investigator must score all abnormal laboratory values as either clinically significant (CS) or not clinically significant (NCS). Some laboratory values may be outside of the normal value range because of the underlying disease. As in routine practice the investigator should use clinical judgment when considering clinical significance. Clinical significant worsening is defined as any variation in laboratory parameters that has medical relevance and results in an alteration in medical care.

If clinically significant laboratory worsening from baseline is noted, the changes will be documented on the appropriate adverse event form and will be followed as an adverse event consistent with the procedure outlined in Sections 11.1,

11.2, and 11.3. The investigator will also assess the relationship of all clinically significant abnormal values to program drug as being none, remote, possible, probable, or definite.

